2.4 Study endpoints

2.4.1 Primary endpoint:

DFS following LRR resection in patients who present without distant metastasis, stratified according to the type of surgery performed for the primary breast cancer (BCS and radiotherapy vs. mastectomy).

2.4.2 Secondary endpoint:

-PFS in patients who present with LRR with distant metastasis.

-OS in patients with LRR +/- DM at presentation.

3. Definitions

For the purpose of this study, LRR is defined as diagnosis of invasive breast cancer or ductal carcinoma in situ in the ipsilateral breast (if applicable)/skin/chest wall/regional nodes (axilla/internal mammary/supraclavicular/infraclavicular) following previous breast cancer treatment with curative intent.

4. Methods

This is a prospective observational multicentre longitudinal cohort study. This will be a national research study in collaboration with the Association of Breast Surgery (ABS) Academic and Research committee, the Mammary Fold Academic and Research Collaborative (MFAC) committee, and the UK Breast Cancer Trainees Research Collaborative Group (BCTRCG).

The study will have 3 main phases;

- 1. National practice questionnaire on current management of patients diagnosed with LRR by breast MDTs across UK.
- Development of a national prospective cohort of patients newly diagnosed with LRR
 +/- DM in order to document management details for each patient with respect to their original and recurrent cancer.
- 3. Evaluating oncological outcomes of the study cohort at 3 and 5 years by collation and analysis of the data submitted from the participating centres.

4.1 National practice questionnaire

The MARECA study National Practice Questionnaire (NPQ) will consist of scenario-based questions (see Appendix) for the breast cancer multidisciplinary teams (MDTs) at the participating centres. It aims to document the current stated practice of breast cancer LRR management, and is designed to capture data on practice variations and areas of uncertainty in patient management. A trainee lead (specialty training registrar or specialty doctor) at each centre will be identified (via MFAC and BCTRCG) who will be asked to complete the questionnaire at the weekly breast MDT meeting and hence ensuring maximal input from all MDT members. The trainee lead will document the number of participants present at the MDT meeting, as well as the MDT composition (e.g. breast surgeons, oncologists, histopathologists, and radiologists). Trainee led research collaboratives have been successful in gaining high response rates for such national practice questionnaires (e.g. iBRA study[62]). The NPQ will be available online (www.surveymonkey.com) to enable ease of completion by each MDT and will be compatible with the current remote pattern of MDT meeting function (as a result of the coronavirus pandemic).

The NPQ will be completed by the participating sites between February and August 2021 prior to the commencement of the prospective cohort study. It has been developed to explore each MDT approach on the following themes;

- Pre-operative investigations.
- The type of breast and axillary surgery offered based on common clinical scenarios.
- Potential factors influencing the decision to offer repeat BCS.
- The type of systemic therapy and radiotherapy offered to treat LRR.

4.2 National prospective cohort study

All UK breast units will be invited to participate through ABS, MFAC, and BCTRCG. The study will also be included in the iBRA-NET research portfolio (https://www.ibra-net.com/mareca). The study will be rolled out nationally for 24 months from November 2021 with the aim of recruiting consecutive eligible patients diagnosed with LRR +/- DM in at least 50 participating UK breast units. The study has been designed to collect information about tumour characteristics and treatment details for the patient's original and recurrent cancer. The study aim is to determine long term prognosis in patients diagnosed with LRR, which will require patient consent. Therefore, ethical approval will be (www.Hra-

decisiontools.org.uk/research) sought to include all participating centres via the Integrated Research Application System (IRAS).

A unit trainee lead will act as an associate principal investigator (pending application outcome for NIHR CRN portfolio status), who will be supervised by the principal investigator (PI, either consultant breast surgeon or oncologist) for each unit. For units without trainees, a designated member of the Clinical Research Network (CRN) research team will act in this role. The PIs will therefore have support in order to recruit and consent eligible patients to the study, as well as complete the Case Report Form (CRF) in order to determine;

- Modality of radiological staging investigations used and determination of the rate of detection of distant metastasis.
- Proportion of patients undergoing repeat breast conserving surgery for in breast recurrence.
- Proportion of patients undergoing repeat sentinel lymph node biopsy, techniques used, and their success rate in terms of sentinel lymph node re-identification.
- Adjuvant treatment modalities used to treat the LRR.
- Proportion of patients undergoing breast surgery for locoregional recurrence in the presence of distant metastasis.

4.2.1 Patient recruitment

Eligible patients (see section 4.6) will be identified at the breast MDT meeting or in breast and oncology clinics by the clinicians directly involved in the patient's care. As part of the direct clinical team, the trainee lead, an appropriately trained member of the team (including research nurses or trials assistants, as per the delegation log), or consultant breast surgeon or oncologist at each unit will discuss the option of study participation with the patient at the clinic and provide a study patient information sheet. This is in accordance with Good Clinical Practice (GCP) guidelines and will have been documented and approved by the Principal Investigator on the delegation log. Identified patients may also be invited to participate using the approved invite letter which can be posted to patients along with the PIS. This will be used to improve the patient identification/approach pathway by providing an additional opportunity for patients to participate in the study. The Patient Invitation Letter v1.0 dated 25 May 2022 incorporates a sentence for the research nurse to be allowed to contact the patient to check if the patient is interested in the study.

19

Patients will be given sufficient time to consider the study information and ask any questions they may have about participation. For patients who agree to participate in the study, they will sign and date the latest approved version of the informed consent form enabling the study specific data collection to proceed. Written consent can be taken by the Principal Investigator, a trainee lead or an appropriately trained member of the team (this may include research nurses or trials assistants). The completion of the consent form may occur during the patient's scheduled hospital visits so not to incur additional hospital visits as a result of agreeing to participate in the study. To reduce burden, patients can also be offered the option to consent the same day as approach if they feel they have had sufficient time to consider the study and the HCP taking consent if happy that they have full understanding. Patients may also consent by post following invite in person or having been approached by the approved invite letter and accompanying PIS.

4.2.2 Prospective data entry

The trainee lead, a designated member of the CRN research team, or consultant breast surgeon or oncologist will be responsible for the prospective data collection which will involve recording patient data that is routinely collected as part of standard clinical practice. The data collection will involve accessing the hospital electronic records or patients' notes to document details about the management of the initial and recurrent cancer (see section 5). This will include reviewing the patient's clinic letters, imaging and pathology reports, operation notes, MDT meeting recommendations, and any other relevant information relating to the patient's cancer treatment. Data will be recorded in a pseudonymised format using a unique alphanumeric study identification number on a secure web-based database (REDCap) designed by Vanderbilt University[63, 64] (http://www.projectredcap.org/). Each participating unit will have individual access to add data to the central REDCap database for the study. The data from each unit will have a unique designated ID, which will be used as a prefix for the patient ID (e.g. SJUH01).

4.3 Evaluation of the initial cancer management

Data collection about the original cancer management will aim to identify known risk factors for LRR (see section 1.2). This will involve examination of the tumour characteristic and the treatment received for the initial cancer. NICE guideline[35] on 'early and locally advanced breast cancer: diagnosis and management (NG 101)' provides recommendations about which patients should be offered particular adjuvant treatments based on the tumour

characteristics and the surgery performed. Therefore, the receipt of, as well as compliance with, the recommended adjuvant treatment will be explored with regards to the management of the patient's original cancer.

4.4 Oncological outcome evaluation

Given that trainees rotate regularly to different hospitals within their respective deaneries, the latter phase of the study examining oncological outcomes at 3 and 5 years will be led by the consultant principal investigators with support from the local research nurses and clinical trial assistants. The following information will be sought from the participating units;

Oncological outcome dataset at 3 and 5 years after LRR diagnosis

-Patient Alive? (Yes/No)

-If No, was it related to breast cancer? (Yes/No; If No what was the cause of death)

-Date of death

-Any further LRR +/- distant metastasis

-Date of further LRR

-Date of distant metastasis

Collection of the above data will enable determination of the patient's disease free survival (DFS), disease specific survival (DSS), progression free survival (PFS), and overall survival (OS). We would not anticipate direct patient contact for study purpose during this follow up period. In cases where the required information is missing or unclear, the research team may contact the patient or their General Practitioner via telephone.

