1.1 The current national status

Breast cancer is diagnosed in approximately 55,000 women per year in the UK (2015-2017; Cancer Research UK[1]) and 5 year survival for all breast cancer patients is favourable at 86.6% as a result of advances in systemic treatment and implementation of the NHS breast screening programme[2]. However, despite this high survival rate, a proportion of patients continue to return to the breast clinic due to cancer recurrence within the conserved breast, ipsilateral skin or chest wall following mastectomy, or in the ipsilateral axillary, supraclavicular, infraclavicular or internal mammary lymph nodes. These cancer recurrences are collected termed locoregional recurrence (LRR). Reflecting the improved cancer treatments, LRR rates are declining. A population based study in Netherlands[3] followed up 1143 patients between 1988 and 2010, and demonstrated that the 5 year local recurrence rate had fallen from 9.8% to 3.3% (comparison of patients diagnosed in 1988-1998 versus 2006-2010). However, recurrences can occur at any time after the original cancer treatment, and a 10 year cumulative LRR incidence of 8% has been reported by a registry-based study in Germany, who followed up patients diagnosed with breast cancer between 1999 and 2009[4]. In the UK, patients who are diagnosed with LRR should be entered into the National Cancer Outcome and Services Dataset (COSD) and to the Cancer Waiting Time (CWT) treatment dataset. However, the reliability of the UK national cancer registries in capturing data about patients diagnosed with LRR requires evaluation as it may be under reported. The 2020 annual report of the National Audit of Breast Cancer in Older Patients (NABCOP) highlights this issue[5]. This audit analysed data from existing routine data sources such as COSD. The 2020 NABCOP annual report determined that for women who died from breast cancer, a high proportion of these patients did not have records registering prior breast cancer recurrence.

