Power calculation was performed to determine sample size in each group (patients treated with mastectomy versus BCS and radiotherapy for the initial cancer), using logistic regression analysis to adjust for other covariates stated in the background section (tumour and nodal staging, molecular receptor profile, and tumour grade). This calculation has determined that the estimated sample size for each group would be 165 patients. Therefore, a subset of 330 patients diagnosed with LRR without distant metastasis will require recruiting to the study to determine whether patient prognosis differs according to the type of breast cancer surgery performed for the initial cancer. This falls well within the minimum patient recruitment target of 500 patients who are diagnosed with LRR +/- distant metastasis.

Kaplan Meier survival analysis will be performed at the two study time points (3 and 5 years after diagnosis of LRR). We will determine DFS/PFS/OS for the study participants. DFS will be determined for patients diagnosed with LRR without associated distant metastasis at presentation who then subsequently undergo LRR resection. PFS will be determined for patients diagnosed with LRR with associated distant metastasis at presentation. OS will be determined for the whole study cohort (i.e. patients diagnosed with LRR with or without associated distant metastasis at presentation). We will perform Cox proportional hazards regression for multivariate analysis and log-rank tests for univariate analysis, including potential prognostic factors as variables of interest.

9. Publication and authorship policy

All presentations and publications will be made on behalf of the MARECA study steering group. The steering group will be responsible for drafting manuscripts and preparing them for publication. Three levels of authorship are proposed based on degree of study participation:

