She now presents with a 1.5cm mastectomy skin flap invasive recurrence which is mobile. Staging is clear and she undergoes wide local excision of the skin flap and axillary surgery. Her resection margins are clear with negative lymph nodes. If this recurrent cancer was a grade 2 ER+HER2- IDC, would your MDT recommend adjuvant chemotherapy for this patient?

Always/Usually/Occasionally/Never

-If your unit offers Ki-67 testing, does your unit perform Ki-67 testing on the recurrent cancer in order to inform adjuvant chemotherapy decision-making for this patient?

Always/Usually/Occasionally/Never (Ki-67 test only utilised for primary breast cancer)/Not applicable as Ki-67 test not routinely offered at the unit

-Would your MDT recommend radiotherapy to the chest wall for this patient?

Always/Usually/Occasionally/Never

-For this scenario, if the patient had instead developed the ER+HER2- local recurrence 3 years after her primary breast cancer surgery (i.e. whilst still on adjuvant endocrine therapy), what adjuvant treatment(s) would your MDT recommend?

- Continue with current endocrine therapy + consider chemotherapy
- Continue with current endocrine therapy + no chemotherapy
- Switch endocrine therapy + consider chemotherapy
- Switch endocrine therapy + no chemotherapy
- No further endocrine therapy + consider chemotherapy
- No further endocrine therapy + no chemotherapy
- Other (please specify)

-For this scenario, if at the time of the recurrent cancer (ER+HER2- IDC) resection, she was instead found to have 1/3 macrometastasis in her axillary lymph node, would your MDT recommend adjuvant chemotherapy for this patient?

Always/Usually/Occasionally/Never

-For this scenario, if the patient had instead developed a recurrent cancer which was grade 3 triple negative IDC (and node negative), would your MDT recommend adjuvant chemotherapy for this patient?

Always/Usually/Occasionally/Never

Patient follow up policy

-Are patients in your unit followed up in the clinic after treatment for breast cancer LRR?

- No routine follow up
- Surgical clinic
- Oncology clinic

- Both surgical and oncology clinic follow up
- Other (please specify)

-What is the total duration of clinic follow up for these patients?

- 1 year
- 2 years
- 3 years
- 4 years
- 5 years
- No follow up protocol with individualised follow up
- Other (please specify)

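### The 3- and 5-year outcome dataset has no last-known-status dates and no unknown/lost answer, so censoring times cannot be derived for patients whose status is unconfirmed

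*Protocol*

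**What the plan says.** Section 4.4 sets out what units return 3 and 5 years after diagnosis of the locoregional recurrence (LRR). The vital status item is "Patient Alive? (Yes/No", with those two answers only. Cause and date of death follow if the patient has died. The disease item is "Any further LRR +/- distant metastasis", with no answer categories given, followed by the date of further LRR and the "Date of distant metastasis". The list is then declared sufficient: "Collection of the above data will enable determination of the patient's disease free survival (DFS", and the sentence goes on to DSS, PFS and OS.

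Other provisions that bear on the point:

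- **Source of the data.** Section 7 has the local team read the hospital electronic system at 3 and 5 years. Section 4.4 adds: "We would not anticipate direct patient contact for study purpose during this follow up period". A telephone call to the patient or GP is allowed, but not required, where information is lacking or ambiguous.
- **Completeness.** Section 6 makes every field compulsory. Section 7.3 reports the number of patients lost to follow-up, without dates.
- **Withdrawal.** Section 10 keeps data gathered before withdrawal, and section 10.2 records the reason. The outcome list in 4.4 has no withdrawal date.
- **Analysis.** Section 8 states: "Kaplan Meier survival analysis will be performed at the two study time points (3 and 5 years after diagnosis of LRR", with log-rank tests and Cox regression.

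**The concern.** Kaplan-Meier and Cox methods need, for every patient without an event, the date up to which that patient was known to be event-free. The listed dataset holds no such date. A patient with no further LRR, metastasis or death contributes no date at all, and the only value left to use is the nominal 3- or 5-year anniversary. That value is right when status was confirmed at the anniversary. It is wrong when the record simply went quiet some time before.

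The form cannot tell these two patients apart. With compulsory fields and only Yes or No for vital status, a site holding a silent record has no listed way to say that it does not know. Such a record may also not look ambiguous, so the optional call need not be triggered.

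The primary endpoint, DFS by type of initial surgery, is exposed because it rests on the absence of a recorded recurrence. If records go quiet more often in one surgery group than in the other, the comparison itself could shift.

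**Working it through.** The protocol gives no loss rate and no expected bias, so there is no figure of its own to reproduce. The following is illustrative.

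**Inputs.** 5-year DFS S = 70% (section 8, approximate). Group values of 80% and 60% (section 8). Assumptions not in the documents: a constant hazard, and a share p of patients whose records stop at 2 years, with p = 10, 20 or 30%.

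**Step 1. Event-free at 2 years.** 0.70^(2/5) = 0.867.

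**Step 2. Later events unseen, silent records counted event-free to 5 years.** Recorded DFS = (1 − p) × 0.70 + p × 0.867.

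- p = 10%: 0.630 + 0.087 = 71.7%
- p = 20%: 0.560 + 0.173 = 73.3%
- p = 30%: 0.490 + 0.260 = 75.0%

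The excess is 1.7 to 5.0 points. With p = 10% in one surgery group and 30% in the other, a difference of 75.0 − 71.7 = 3.3 points appears where none exists.

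**Step 3. A different loss pattern.** Let a share L be lost uniformly over 0 to 5 years. Recorded DFS = 1 − [(1 − L)(1 − S) + L × F], where F = 1 − (1 − S)/(−ln S). For L = 20%:

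- S = 80%: F = 0.104, recorded 81.9%
- S = 60%: F = 0.217, recorded 63.7%

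The planned 20-point difference becomes 18.3 points. With 5% lost in one group and 20% in the other, it lies between 16.8 and 21.0 points, depending on which group loses more. In simulation with 20% lost, Kaplan-Meier censored at the date of loss returned 79.96%, 69.96% and 60.07% for true values of 80%, 70% and 60%.

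**Step 4. Is censoring at the last assessment always right?** Suppose instead that patients discharged at 2 years who later recur come back and are counted, while those who stay well are censored at 2 years. Then Kaplan-Meier at 5 years = 0.867 × (1 − p) × 0.70 / (0.867 − 0.70p).

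- p = 10%: 0.867 × 0.63 / 0.797 = 68.5%
- p = 20%: 0.867 × 0.56 / 0.727 = 66.8%
- p = 30%: 0.867 × 0.49 / 0.657 = 64.7%

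Set against a true 70%:

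| p | Unseen later events, anniversary | Unseen, last assessment | Seen later events, anniversary | Seen, last assessment |
|---|---|---|---|---|
| 10% | 71.7 | 70 | 70 | 68.5 |
| 20% | 73.3 | 70 | 70 | 66.8 |
| 30% | 75.0 | 70 | 70 | 64.7 |

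Neither rule is safe alone, and without the missing dates only the anniversary rule can be applied.

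**PFS.** The protocol gives no PFS rate. The excess in Step 2 is p × (S^(2/5) − S), so it has the same sign for PFS and the same size only if S is also 70%.

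**The case against.** The strongest reply is that the protocol nowhere counts lost patients as event-free. It foresees gaps, permits a call to the patient or GP, tallies losses and keeps data up to withdrawal. Censoring rules usually sit in a statistical analysis plan, which is not at hand. An unresolved patient could be left missing, or censored at the 3-year return. All of this stands, so the overstatement is conditional. What does not follow is that an analysis plan can repair the gap: it can define a rule, but it cannot censor at a date that was never collected.

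Three stronger readings are tempting and are not supported:

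- **That discharged patients will be treated as disease-free to 5 years.** The appendix questionnaire offers "No routine follow up" and follow-up of 1 to 4 years among its answers. These are answer options, listed beside 5 years and individualised follow-up. They are not observed unit policies. Discharge from clinic also does not stop the hospital record, since a patient who recurs may return.
- **That the protocol admits hospital notes miss recurrences.** Section 1.1 says that among women who died of breast cancer "a high proportion of these patients did not have records registering prior breast cancer recurrence". That describes an audit of national routine datasets. The protocol gives it as a reason not to rely on such sources, and this study reads local records.
- **That OS is overstated in the same way as DFS.** A patient confirmed alive at the 3- or 5-year point is validly censored there. OS is biased only if alive is entered without confirmation, and nothing directs sites to do that.

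The objection that censoring DFS at the last clinic or imaging visit can bias it downward is also correct, as Step 4 shows. With 10% discharged in one group and 30% in the other, that rule alone would create a false difference of about 3.9 points.

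**Conclusion.** The point holds as a defect in the listed dataset. Section 4.4 says its items will yield DFS, PFS and OS. For patients whose status is not confirmed at 3 or 5 years they do not, because no last-known-status date, unknown/lost answer or withdrawal date is listed.

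The consequence is conditional. If silent records are entered as alive and recurrence-free, DFS is overstated by about 2 to 5 points when 10 to 30% of records stop at 2 years and later events go unseen. This assumes a constant hazard and a true 5-year DFS of 70%, and the loss rates are assumptions without a source in the protocol. PFS is exposed in the same direction. A bias in the surgery comparison needs loss to differ between the groups or to act on different event rates, and its direction cannot be stated in advance.

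**What to change.** Add to the 3- and 5-year form:

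- the date last known alive;
- the date disease status was last known, and its source (clinic, imaging, GP or patient contact);
- an unknown/lost answer for both vital status and recurrence status;
- the date of withdrawal.

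Make the patient or GP call that section 4.4 already permits the required step when status is not current at the 3- or 5-year point.

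State the censoring rule. For OS, censor at the date last known alive. For DFS and PFS, censor at the anniversary when status there is confirmed from any source, and otherwise at the date disease status was last known. Add a sensitivity analysis under the alternative rule (anniversary versus last assessment), since the two err in opposite directions. Report completeness of follow-up by initial surgery group.

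The cost is slightly more abstraction from records already being read, some calls already allowed, and slightly wider intervals. Timing favours acting at this version. Section 4.2 starts recruitment in November 2021 and section 4.6.1 admits diagnoses up to 6 months old, so the earliest 3-year point is about May 2024, two years after the version date of May 2022. Reconstructing these dates afterwards across at least 50 units would be harder.

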2.3 Objectives

 To carry out a national survey of UK breast units in order to establish the current stated practice of breast MDTs regarding the management of patients with locoregional recurrence and identify any potential geographical variations. 2. To establish a prospective cohort of breast cancer patients diagnosed with locoregional recurrence +/- distant metastasis in order to:

- i) Describe current management including:
 - Use of radiological staging investigations and the proportion of patients found to have distant metastasis (DM) at presentation.
 - Surgical management including the use of repeat BCS and SLNB.
 - Use of systemic therapies and radiotherapy used to treat locoregional recurrence.
- ii) Investigate risk factors associated with LRR development including those related to the primary breast cancer and its management.
- Determine the following oncological outcome at 3 and 5 years, and evaluate prognostic factors;

-Disease Free Survival (DFS) for patients diagnosed with LRR without associated distant metastasis at presentation.

-Progression Free Survival (PFS) for patients diagnosed with LRR with associated distant metastasis at presentation.

-Overall Survival (OS) for patients diagnosed with LRR with or without associated distant metastasis at presentation.

 iv) Stratify LRR as a true recurrence (TR) or a new primary (NP) breast cancer using clinical classification systems and explore if this distinction affects oncological outcomes.

3. To determine the feasibility of designing a future potential translational study. Patients enrolled in the study will be invited to provide optional consent for permission to access archival tissue samples (or slides) of both the primary cancer and the locoregional recurrence. This would permit comparison of clinical and genomic classification of locoregional recurrences (true recurrence or new primary) against patient survival outcome.

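### The 3- and 5-year outcome dataset has no item or date for progression of existing disease, so it cannot yield PFS in its usual sense for the metastatic group, although Section 4.4 says it will

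*Protocol*

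**What the plan says.** Section 2.4.2 names as a secondary endpoint "PFS in patients who present with LRR with distant metastasis". Section 2.3 gives the same population among the objectives: "Progression Free Survival (PFS) for patients diagnosed with LRR with associated distant metastasis at presentation". Section 8 repeats it in the analysis plan: "PFS will be determined for patients diagnosed with LRR with associated distant metastasis at presentation". No section assigns PFS to anyone else, and no section defines progression or PFS.

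Section 4.4 sets out the outcome dataset at 3 and 5 years after LRR diagnosis. It asks whether the patient is alive, whether a death was related to breast cancer (and the cause if not), and the date of death. The disease items are "Any further LRR +/- distant metastasis", "Date of further LRR" and "Date of distant metastasis". The section then concludes that collecting these items makes it possible to determine "disease free survival (DFS), disease specific survival (DSS), progression free survival (PFS), and overall survival (OS").

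Section 7 ties the later record access to this list: site teams open the hospital records at 3 and 5 years to record the outcome that Section 4.4 specifies.

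**The concern.** In a patient who presents with metastatic disease, the usual progression event is growth of lesions that are already known: the metastases, or the LRR if it was left in place. The listed disease items describe new events. If sites return exactly what Section 4.4 asks for, progression of known disease is never recorded, and a later analysis plan can define PFS but cannot recover dates that were not collected.

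At stake is one of the two listed secondary endpoints. A measure that omits a main type of event would be published as PFS and read against PFS from other studies of metastatic breast cancer. The protocol also states that its data suffice, so sites and analysts have no prompt to look for the gap.

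**Working it through.** The protocol gives no figure to reproduce for PFS: no power, alpha or event count. The check is a mapping of what PFS needs in this population against what is collected, in Section 4.4 and in Section 5 (items 1.1 to 3.52).

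| Event needed for PFS | Collected? | Where |
|---|---|---|
| Growth of known metastases | No | No item in 4.4 or Section 5 |
| Growth of an unresected LRR | No | No item in 4.4 or Section 5 |
| New local or regional lesion | Yes, with date | 4.4, further LRR |
| New distant lesion | Ambiguous | 4.4, date of distant metastasis |
| Death | Yes, with date | 4.4 |

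**Unresected disease is foreseen.** Item 3.21 asks whether a patient with metastasis had surgery and lets the answer be no. Item 3.24 lists unresectable LRR and metastasis found on staging among the reasons for no surgery. Section 1.5.3 says that resection was traditionally not considered in these patients except for palliation, and that the number now having it in the UK is unknown. The unresected share therefore cannot be stated.

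**The distant item is ambiguous.** Items 3.19 and 3.20 record presence and site of metastasis at staging, but no date. Section 6 requires every field to be completed. Section 4.4 does not say whether a metastasis already present at LRR diagnosis should be entered again.

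**Direction of the error.** Suppose the distant item is used only for new lesions. For each patient:

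- derivable time = min(further LRR, new metastasis, death)
- PFS = min(growth of existing disease, further LRR, new metastasis, death)

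The second minimum is taken over the same events plus one more, so derivable time ≥ PFS for every patient. It is strictly longer for anyone whose known disease grew first.

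**Size of the group, for scale only.** The protocol gives no expected number, so two anchors are shown:

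- Section 8 needs 330 patients without distant metastasis, out of a target of at least 500. If exactly 330 of 500 are non-metastatic: 500 − 330 = 170, and 170/500 = 34%.
- The 2011 pilot audit in Section 1.1 found 137 patients with LRR only and 114 with locoregional and distant recurrence. 137 + 114 = 251; 114/251 = 45.4%; 0.454 × 500 = 227.

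**Other endpoints.** Deaths and their dates serve OS, cause of death serves DSS, and new recurrence or metastasis serves DFS in patients who start without metastasis. The event-type gap is specific to PFS.

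**The case against.** Several objections are fair and limit the point.

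- *PFS can still be computed.* A reader might infer that no PFS can be derived at all. That goes too far: because the protocol never defines PFS, a time to new lesion or death can be built. What stands is that this is not PFS in its usual sense and should not carry the name.
- *The form itself is not shown.* True. The protocol gives a dataset, not the REDCap screens, so the point concerns the dataset that the protocol fixes and declares sufficient.
- *The word for further events may cover metastasis too.* Possibly, and baseline metastases are identifiable from items 3.19 and 3.20. A reader might infer that these patients will be counted as having an event at baseline. The text supports only ambiguity.
- *Sites may telephone the patient or GP.* Section 4.4 allows this where required information is missing or unclear. Progression is not among the required items, so the provision does not fill the gap.
- *There is no last-contact date.* A reader might infer that no Kaplan-Meier curve can be censored. The documents do not support that. The LRR diagnosis date is collected (item 3.1) and status is taken at fixed times from it, so a patient recorded alive and event-free at 3 or 5 years can be censored there. Only patients lost between collection points are affected, and such a field is commonly left to the analysis plan or case report form.
- *PFS is secondary and unpowered.* This limits the consequence, but the statement in Section 4.4 remains wrong as written.

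**Conclusion.** The point holds in this form: Section 4.4 claims more than its list delivers. For the only population to which PFS applies, progression of existing disease is neither recorded nor dated. The derivable measure overstates PFS, provided that the distant item is used only for new lesions.

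The amount cannot be quantified from the protocol. A reader might infer something like a doubling, but that would rest on assumed median PFS and OS values that appear nowhere in the document, and on ignoring the new lesions that are captured.

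The affected group is 170 to 227 of 500 (34% to 45%) under the two anchors. Neither is a protocol estimate. The lower one assumes a split exactly at the 330 requirement; the upper one assumes that a 15-unit audit carries over to a consented cohort. It would be wrong to take 45% as established.

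The primary DFS endpoint, OS and DSS are not affected by the progression gap.

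**What to change.** Before the 3-year returns, amend the Section 4.4 dataset:

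1. Add a progression item: yes or no, existing or new lesion, local or distant.
2. Add the date of first progression and its basis (imaging or clinical).
3. State that metastases present at LRR diagnosis are not entered under the date of distant metastasis.
4. Define PFS to match these items.

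If progression dates prove unobtainable from hospital records, rename or drop PFS consistently in Sections 2.3, 2.4.2, 4.4 and 8, and report OS for this group.

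A date last known alive or event-free would be a useful minor addition for patients lost between collection points; its absence is not a separate error.

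The cost is a few extra REDCap fields, drawn from records that sites already open at 3 and 5 years, and slightly more abstraction time per metastatic patient. Making the change before the returns avoids going back to the notes across 50 or more units.
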